We plan to accomplish our goal by pursuing the following specific aim and testing the associated hypothesis:

Aim:

Determine the frequency of past CL wearers who failed because dryness or CL discomfort who can comfortably wear DT1. Hypothesis 1: At least 50% of past CL wearers can comfortably wear DT1 at one month (Positive Visual Analog Scale Score (VAS) based upon +50/50 VAS scale with 0 as neutral).

Exploratory Outcomes

A Likert questionnaire will be used to determine the following patient-reported outcomes at 1 and 6 months: 1. Likelihood of continuing to wear DT1, 2. Overall satisfaction while wearing DT1, Overall vision while wearing DT1, 3. End of day comfort while wearing DT1. The SPEED questionaries will also be used to determine the frequency of DT1 wears who can comfortable wear DT1 (scores ≤ 3).³

III. STUDY DESIGN

Participants

This 6-month, three-visit clinical study will be conducted at the University of Alabama at Birmingham (Birmingham, AL, USA), the Southern College of Optometry (Memphis, TN), and ProCare Vision Center (Granville, OH). One month will be the primary outcome timepoint because Young et al. found that most participants who dropped out of CLs in their study dropped out by 1 month (23% dropout).⁴ Participants will also be called at 6-months like in Young et al.’s study to determine the ultimate CL success frequency. This 6-month survey will be an exploratory outcome that will supported by the investigators (not Alcon). Participants will be recruited via clinic records, email, and fliers. Participants will be prescreened with an IRB approved phone script prior to the study visit to help determine if they qualify for the study. The reason why all potential participants dropped out of CLs will be recorded even if they are not included in the study. Adult, 18-

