This pilot study is proposing a sample of 60 participants (20/site) to estimate the initial frequency that participants can comfortably wear DT1 at 1 month. This sample size was selected because it is a feasible number of participants that can be recruited while also providing enough data to determine if at least 50% of participants can comfortable wear DT1 CLs. These should also be enough participants to evaluate exploratory patient reported outcomes such as the likelihood of continuing DT1 after completing the study. An additional 5 participants per site are being requested in case someone fails the glasses prescription requirements for this study. Additional participants will only be recruited if needed.

Surveys and Clinical Tests

Visit 1: Baseline

1. Participant History, Eligibility, Informed Consent: Participants will be asked to repeat the IRB approved screening survey at the study visit to verify that they are still eligible for the study. All participants will be screened with the SPEED questionnaire to understand their initial eye comfort (scores ≤ 3 required).⁶ The SPEED is being selected because it has been validated in both CL and non-CL wearers. All relevant patient demographics will be collected via a questionnaire developed by the investigators. Non-eligible participants will be dismissed at this time or rescheduled depending upon the reason for ineligibility. Eligible participants will be enrolled, consented, and requested to sign a privacy document.

2. Visual Acuity with Spectacles: Visual acuity will be measured with a Bailey-Lovie high-contrast chart.

3. Manifest Refraction: The investigator will determine the participants' refractive error with a phoropter, and binocular balance will be performed if best-corrected visual acuity is equal in between eyes. No more than 1.00 D of sphere will be added beyond the initial blur balance starting point.

4. Slit-Lamp Biomicroscopy: The investigator will use a slit-lamp biomicroscope to document normal and/or remarkable findings of the anterior eye structures: eyelashes (blepharitis), eyelids, conjunctiva, and cornea.

5. CL Fitting: Participants will be fit in DT1 sphere CLs. The CLs will be evaluated for centration, movement, coverage, and CL power adjustments will only be made if they improve Snellen visual acuity.

Visit 2: 1 Week

1. Stannard Patient Evaluation of Eye Dryness (SPEED): The SPEED questionnaire will be completed.

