2. Visual Acuity with CLs: Visual acuity will be measured with a Bailey-Lovie high-contrast chart.

3. Slit-Lamp Biomicroscopy: The investigator will use a slit-lamp biomicroscope to document normal and/or remarkable findings of the anterior eye structures: eyelashes (blepharitis), eyelids, conjunctiva, and cornea.

4. CL Evaluation: The CLs will be evaluated for centration, movement, and coverage, and lens power adjustments will only be made if they improve Snellen visual acuity.

Visit 3: 1 Month (Primary Endpoint)

1. Stannard Patient Evaluation of Eye Dryness (SPEED): The SPEED questionnaire will be completed.

2. Visual Analog Scale (VAS): The VAS will be completed.

3. Investigator Survey: An exploratory questionnaire that probes topics such as vision, dryness, comfortable wear time, and willingness to continue wearing the contact lenses will be completed.

4. Visual Acuity with CLs: Visual acuity will be measured with a Bailey-Lovie high-contrast chart.

5. Slit-Lamp Biomicroscopy: The investigator will use a slit-lamp biomicroscope to document normal and/or remarkable findings of the anterior eye structures: eyelashes (blepharitis), eyelids, conjunctiva, and cornea.

6. CL Evaluation: The CLs will be evaluated for centration, movement, and coverage, and lens power adjustments will only be made if they improve Snellen visual acuity.

7. Study Completion: The participants will be compensated for their time, and they will be released from the clinical segment of the study. If participants like the CLs, they will be given a prescription for the CLs, though they will be required to buy their own CLs. The participants will also be educated that they will be called in 6 months to understand their wearing experience if they decide to continue wearing DT1 CLs.

Data Analysis

All data will be analyzed with Stata/IC 15 (StataCorp LLC; TX, USA). The frequency of participants who have comfortable VAS scores will be calculated at both the 1-month (primary outcome) and 6-month visits (exploratory outcome). The frequency of each Likert question and the SPEED will also be calculated.

Training of Study Personnel

Prior to enrolling any participants all examiners will participate in a training session developed by [name], OD, PhD. This full investigator meeting will ensure that all study investigators are performing the

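### The 6-month call is unconditional in the design section but appears limited to DT1 continuers at Visit 3, so the exploratory success frequency risks being a continuers-only figure

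*Combined protocol and SAP*

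**What the plan says.** Section III (Study Design, Participants) states "Participants will also be called at 6-months", with no restriction on who is called. The purpose given, following an earlier multi-centre study of lapsed wearers, is for this "study to determine the ultimate CL success frequency". The same paragraph sets its status: "This 6-month survey will be an exploratory outcome", supported by the investigators rather than the company.

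Visit 3, item 7 (Study Completion) describes what participants hear when they are released: they will be "called in 6 months to understand their wearing experience if they decide to continue wearing DT1 CLs". The sentence before it sets the terms of further wear: "If participants like the CLs, they will be given a prescription for the CLs, though they will be required to buy their own CLs".

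Data Analysis covers both timepoints in one sentence: "The frequency of participants who have comfortable VAS scores will be calculated at both the 1-month (primary outcome) and 6-month visits (exploratory outcome". It gives no denominator and no rule for participants who have stopped DT1 or cannot be reached.

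Two other places bear on continuation. The Sample Size section lists "the likelihood of continuing DT1 after completing the study" among the exploratory outcomes, and the Visit 3 investigator survey asks about willingness to go on wearing the lenses.

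**The concern.** The stated 6-month question is how many refitted dropouts succeed in the end. That needs everyone who was refitted in the denominator. If staff follow the Visit 3 wording, 6-month VAS scores will exist only for people who chose to continue. By the plan's own terms, that group is selected on liking the lens and on being willing to pay for it. Liking the lens is close to the outcome being measured, so a comfort frequency in that group would tend to be high whatever happened to the rest.

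The loss also cannot be repaired. Someone not called at 6 months cannot be asked later about their status at that time, and a denominator chosen after the data are seen is less credible than one fixed beforehand.

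**Working it through.** **Figure to reproduce.** The plan gives no 6-month sample size, rate or test, so there is none. The only count to check is the planned sample: 3 sites × 20 = 60, which agrees with the Sample Size section.

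**The passages side by side.**
- Participants: a call at 6 months, no condition, purpose is the final success frequency.
- Visit 3, item 7: a call at 6 months, followed by a clause about deciding to continue. The natural reading is that the clause governs who is called. It can also be read as governing only the wearing experience to be discussed.
- Data Analysis: speaks of participants, without saying which.
- Exploratory Outcomes (Section II): the 6-month Likert items on satisfaction, vision and end-of-day comfort are framed around wearing DT1, and the SPEED frequency is described among DT1 wearers. Someone who has stopped has no natural answer to these.

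Nothing else in the documents settles who is called or counted.

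**Size of the difference.** Let N = 60 fitted (Sample Size section), c = number continuing, s = comfortable continuers, q = success rate among non-continuers. The documents give none of c, s or q, so all three are assumptions.

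- Continuers-only frequency = s/c
- All-fitted frequency = [s + q(N − c)]/N
- Gap = (1 − c/N)(s/c − q)
- At q = 0 the ratio of the two is N/c = 60/c

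With about 80% of continuers comfortable:

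| c | s | s/c | s/60 (q = 0) | Gap, q = 0 | Ratio 60/c | Gap, q = 0.20 |
|---|---|---|---|---|---|---|
| 57 | 46 | 80.7% | 76.7% | 4.0 | 1.05 | 3.0 |
| 54 | 43 | 79.6% | 71.7% | 8.0 | 1.11 | 6.0 |
| 46 | 37 | 80.4% | 61.7% | 18.8 | 1.30 | 14.1 |
| 36 | 29 | 80.6% | 48.3% | 32.2 | 1.67 | 24.2 |
| 30 | 24 | 80.0% | 40.0% | 40.0 | 2.00 | 30.0 |

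Gaps are in percentage points. Worked line for c = 46, q = 0.20: all-fitted = (37 + 0.20 × 14)/60 = 39.8/60 = 66.3%, and 80.4 − 66.3 = 14.1.

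The c = 46 row uses the only dropout figure in the plan, 23% by 1 month in the earlier study of lapsed wearers: 0.77 × 60 = 46.2. It is neither a 6-month rate nor a DT1 rate, so it serves only as a reference point.

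Sensitivity to the comfort rate at q = 0:
- c = 54: gap 7.0 points with s = 38 (about 70%) and 9.1 with s = 49 (about 90%).
- c = 30: gap 35.0 points with s = 21 (70%) and 45.0 with s = 27 (90%).

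The gap is zero if everyone continues or if q equals s/c. It is positive whenever continuers do better than non-continuers.

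**The case against.** The best defence is that the two sentences do different jobs. The Participants section states the design. Item 7 reports what participants are told at release and is neither a rule for who is called nor an analysis rule. Read together, they could mean that everyone is called and those still wearing DT1 are asked about it. Data Analysis uses the word participants for both timepoints, so someone without a comfortable score could simply not count as comfortable.

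Much of this stands. A reader might infer that the protocol flatly contradicts itself, or that a continuers-only analysis is planned. The documents support neither. The clause is ambiguous, and no sentence restricts the analysis to continuers. What remains is a risk: the more natural reading of item 7 produces data from continuers only, and no rule elsewhere prevents that.

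A reader might also infer that the primary result is compromised. It is not affected by the call clause. Data Analysis leaves the 1-month denominator unstated too, but that is a separate matter.

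Three further objections limit the point:
- Visit 3 records willingness to continue, so those who decline could be kept in the denominator without a call. That is correct, but no rule says so, and their later wear would be unknown.
- The Likert items about wearing DT1 are properly answered by current wearers. That is also correct, and the fix leaves them so.
- Counting every stopper as a failure mixes cost with comfort, because participants buy their own lenses. This is a real cost. It is met by naming the outcome accurately and recording why people stopped.

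**Conclusion.** The concern holds as a minor point about an exploratory outcome. The two descriptions of the 6-month call need to be reconciled. If calls follow the Visit 3 wording, the 6-month comfort frequency risks being computed among continuers only, which would overstate success among all refitted dropouts whenever continuers do better than the rest. If no non-continuer is a success, the factor is 60/c.

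The actual size is unknown. The range of about 4 to 40 points (3 to 30 if a fifth of non-continuers succeed) rests on assumed continuation of 57 down to 30 out of 60 and comfort of about 80% among continuers. It shows how the two figures diverge and does not predict an error. With high continuation the difference is small.

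The stakes are limited. The survey carries no hypothesis or threshold, the commitment to the funder ends with the 1-month analysis (Section IV), and the planned abstract concerns the primary outcome (Section V).

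**What to change.** 1. In Visit 3, item 7, delete the conditional clause that ends the sentence on the 6-month call, so that it agrees with the Participants section and every fitted participant is called.

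2. In Data Analysis, define the 6-month success frequency as still wearing DT1 and comfortable, with all fitted participants as the denominator. Known stoppers count as not successful, including anyone who declined at Visit 3 and is not reached.

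3. On the call, ask stoppers why they stopped (discomfort or dryness, cost, other) and tabulate the answers, so that stops for cost can be seen apart from stops for discomfort.

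4. Show the remaining unreached participants with best- and worst-case bounds. For example, 35 successes with 6 not reached gives 35/60 = 58.3% to 41/60 = 68.3%.

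5. The Likert items about wearing DT1, and any continuers-only comfort figure, may be reported among current wearers if labelled as conditional on continuing.

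The cost is one deleted clause, a few sentences in Data Analysis, one question on the call, and about 3 to 30 extra short calls (60 − 57 to 60 − 30 under the assumptions above). The 6-month figure will be lower and will reflect cost as well as comfort.
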